We aim to follow up on this previous study, by covertly manipulating the level of energy density of a meal, using the same parameters as the prior study. In this previous study the foods provided were noticeably different to participants, and so underlying preferences and differences in sensory and nutritional aspects of the meals may have influenced the amount consumed. Equally, this study did not measure whether later intake differed following consumption of desserts varying in energy density. For the present study, the foods provided will be variations on the same meal (loaded fries), so participant's expectations of the meals should be comparable. This will help us to understand whether reformulation to approximately 2kcal/g would lead to a reduction in energy intake, or if further reduction, below 1.5kcal/g is required to influence immediate eating behaviour positively by reducing energy intake. Additionally, if there are significant effects of energy density, it is vital to determine whether these changes are compensated for by consumers later on in the day.

Primary objectives: To observe differences in consumption (g/kcal) when participants are given a meal covertly manipulated to be low, medium or high in energy density.

Secondary objective: To measure later food intake, in order to observe any evidence of later compensation in response to experimental condition.

To measure intake over the full day, in order to understand whether one manipulated meal impacts daily energy intake.

Study Information

Hypotheses:

Based on Flynn et al(18), it is hypothesised that as the energy density of the lunch meal increases from low ED to medium ED, the amount of the lunch consumed (g) will remain similar, but due to the increased energy density, the calories consumed will increase.

As energy density of the lunch meal increases from medium ED to high ED, the amount of lunch consumed (g) will decrease, due to people compensating for the increase in energy density (i.e., participants will attend to satiety signals and adjust meal size).

Design Plan

Study type: Experiment - A researcher randomly assigns treatments to study subjects, this includes field or lab experiments. This is also known as an intervention experiment and includes randomized controlled trials.

Blinding: For studies that involve human subjects, they will not know the treatment group to which they have been assigned.

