Participant characteristics will be presented in a table. Data will include age, gender, ethnicity, BMI, highest education level, perceived social status, childhood SEP, compensatory health beliefs and satiety awareness. Continuous variables will be summarised by means and standard deviations, categorical variables will be summarised by counts and percentages.

Primary analyses:

Two repeated-measures, within-subjects ANOVAs will assess lunchtime (manipulated meal) kcal and gram intake across the three conditions. Where significant main effects are identified, post-hoc pairwise comparisons will be performed to identify where these differences exist. Sensory ratings of the three meals will be compared using repeated-measures, within-subjects ANOVAs to assess whether all meals were rated equally. Results will be considered statistically significant at $p<0.05$.

Secondary analyses:

Two repeated-measures, within-subjects ANOVAs will assess later kcal and gram intake (dinner, dessert and snacks) across the three conditions (low ED, medium ED and high ED). Where significant main effects are identified, post-hoc analyses will be performed to identify where these differences exist.

A repeated-measures, within-subjects ANOVA will assess daily energy intake (sum of lunch, dinner, dessert, snacks and additional food) across the three conditions. Where significant main effects are identified, post-hoc analyses will be performed to identify where these differences exist.

To account for multiple comparisons, results for secondary analyses will be considered significant at $p<.01$.

Sensitivity analyses:

We will examine evidence of extreme outliers (+3 standard deviations from the session mean) in grams consumed for each test food, and for any outcomes identified as outliers we will examine the effect of winsorizing the outlier.

If we find evidence that meals differ in sensory ratings then we will also examine if results remain the same when sensory ratings are controlled for in analyses as a covariate.

We will also examine if results remain the same among participants who accurately identify the differences in energy density between foods vs. participants who do not. Alternatively, if only a small number of participants are unable to identify the correct order of energy density then we will examine if results remain the same when excluded.

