We will report whether sensitivity analyses deviate from primary analyses (e.g. if significant findings become non-significant and vice versa).

Transformations: N/A

Inference criteria: Results for primary analyses will be considered significant at $p<0.05$, and to account for multiple comparisons, secondary analyses will be considered significant at $p<0.01$.

Data exclusion: If participants drop out of the study, any data will be excluded from analyses.

Missing data: For participants who complete all three study sessions, it is not anticipated that missing data will be a problem. If there is missing data, participants will be excluded from analyses.

Exploratory analysis:

Other:

Sample size:

A previous study provided three desserts differing in energy density to participants over three consecutive weeks. Grams consumed and kcals consumed for each dessert were recorded. The

influence of energy density on intake (g) was significant ($p < .001$), with a partial eta squared of 0.4 (large effect). The influence of energy density on kcals eaten was also significant ($p < .001$) with a partial eta squared of 0.7 (large effect). As the relative energy density of the meals will be unknown to participants (desserts were familiar in the previous study), it is anticipated that effect sizes will be smaller than observed in the previous study. We will power the present study to be able to detect a medium effect size of $f = 0.25$ through a repeated-measures, within factors ANOVA consisting of three measures at 0.95% power. This will require a minimum sample of 28 participants.

If the findings of the ANOVA show significant differences between the three conditions, post-hoc analyses will be conducted. In the previous study, the smallest effect observed had a Cohens D of 0.52. We will power the present study to be able to detect effects of this size at 0.8% power in post-hoc t-tests, which will require a minimum sample of 32 participants.

Therefore, we will aim to recruit a minimum of 32 participants for this study.

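### A non-significant difference test is the plan's only route to calling the three lunches equally rated, and it also decides whether the sensory-adjusted sensitivity analysis is run

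*Combined protocol and SAP*

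**What the plan says.** Analysis Plan, Primary analyses: "Sensory ratings of the three meals will be compared using repeated-measures, within-subjects ANOVAs to assess whether all meals were rated equally". The threshold is 0.05, with no adjustment across ratings.

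Analysis Plan, Sensitivity analyses: "If we find evidence that meals differ in sensory ratings then we will also examine if results remain the same when sensory ratings are controlled", with the ratings entered as a covariate.

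The Sensory ratings section lists eight visual analogue scales, scored 1 to 100 and completed after the meal: Pleasant, Sweet, Savoury, Salty, Familiar, Filling, Soft and Appetising (visually). The plan gives no margin, confidence interval or equivalence criterion. It does not say which scale, or how many, would count as evidence of a difference, or which ratings would enter as covariates.

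The background explains that in the previous dessert study "underlying preferences and differences in sensory and nutritional aspects of the meals may have influenced the amount consumed". That is a stated reason for now using variations of one dish.

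The sample size rests on intake, not on ratings: "In the previous study, the smallest effect observed had a Cohens D of 0.52", powered "at 0.8% power in post-hoc t-tests, which will require a minimum sample of 32 participants" (0.8% is read here as 80%). The section concludes: "Therefore, we will aim to recruit a minimum of 32 participants for this study".

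**The concern.** A difference test can give evidence that ratings differ. Its failure to do so is not evidence that they are the same, least of all in a sample sized for another outcome. As written, a non-significant ANOVA is the only result that could lead to a statement of equal ratings. The same result means the sensory-controlled analysis is not run.

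This bears on the second hypothesis, that grams eaten fall from the medium to the high lunch because people compensate for energy density. The obvious rival explanation is that the high lunch is liked less. The recipes give it some plausibility. Table 1 shows mince rising from 250 g (5% fat) in the low chilli to 769 g (20% fat) in the high one, fat from 4.8 to 24.5 per 100 g, and moisture falling from 76.1 to 47.2 per 100 g. The ratings are the only data the plan will collect on that rival explanation.

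**Working it through.** **Inputs from the documents.** N = 32; three meals; alpha 0.05; eight scales; d = 0.52 and 80% power for the post-hoc tests.

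**Assumed, because the documents give neither a rating SD nor a correlation.** A true maximum difference of 0.5 SD; between-visit correlation ρ of 0.3, 0.5 or 0.7; sphericity.

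**Step 1: the plan's own N.** Two-sided paired t-test, noncentral t, d read as the standardised paired difference (0.52): N = 32 gives power 0.813. The figure reproduces.

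**Step 2: chance of missing a 0.5 SD difference on one scale.** The repeated-measures F test has 2 and 2 × (32 − 1) = 62 degrees of freedom, with noncentrality λ = N × Σ(μᵢ − mean)² / (1 − ρ), means in SD units.

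- One meal differs (0, 0, 0.5): Σ = 0.1667. At ρ = 0.5, λ = 32 × 0.1667 / 0.5 = 10.67.
- Even steps (0, 0.25, 0.5): Σ = 0.125. At ρ = 0.5, λ = 32 × 0.125 / 0.5 = 8.00.

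| ρ | One meal differs: missed | Even steps: missed |
|---|---|---|
| 0.3 | 33% | 46% |
| 0.5 | 18% | 31% |
| 0.7 | 3% | 10% |

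Simulation agrees. With non-sphericity (epsilon 0.75) the ρ = 0.5 row becomes 27% and 40%. A single paired t-test at a standardised difference of 0.5 misses 22%.

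**Step 3: chance that the adjustment stays off.** The plan does not define the trigger. Suppose any one of the eight scales suffices and only Pleasant truly differs. With independent scales, the chance that none is significant is the miss rate × 0.95⁷, and 0.95⁷ = 0.698.

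- ρ = 0.5: 0.178 × 0.698 = 12% and 0.305 × 0.698 = 21%.
- Simulation with scales correlated 0.3–0.5 changes this little at ρ = 0.5 (about 13% and 22–23%). It gives about 24–36% at ρ = 0.3 and 2–7% at ρ = 0.7.

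**Step 4: chance that it fires when all meals are rated identically.** With independent scales, 1 − 0.95⁸ = 34%. Simulation gives about 30% at inter-scale correlation 0.3 and 24–26% at 0.5.

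**Step 5: effect on the gram result.** Simulated case: the high meal is 0.5 SD less pleasant, energy density has no effect, and the within-person correlation of pleasantness with grams is 0.3–0.5 (assumed). The medium-to-high gram t-test is significant in 10–27% of trials. It is significant together with a non-significant pleasantness ANOVA in about 1–3%.

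**The case against.** A reader might infer that a half-SD palatability difference would often pass as equal and so switch off the adjustment. The documents do not support that. The single-scale miss rates in Step 2 are not the chance that the adjustment is skipped, because another scale may trigger it; Step 3 gives the relevant figures. *Often* would hold only at low correlations, and the documents give none.

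A reader might also infer that the primary results are exposed to many undetected false positives. They are not. What is skipped is a sensitivity analysis, the primary intake ANOVAs are unadjusted either way, and the combination that would mislead arises in about 1–3% of trials under the Step 5 assumptions.

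The plan never says in terms that non-significance will be reported as proof of equality. That is a fair point. Still, the test's stated purpose is to judge whether ratings were equal, and no other criterion is offered.

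The design gives some protection. The Procedure says the recipes were tried repeatedly for equal appeal, liking the test foods is an inclusion criterion checked at screening, and the lunches are versions of one dish eaten by the same people in randomised order. This mitigates the problem, but the pre-testing comes with no data or criterion, and liking the foods in general does not show that the three versions are liked equally.

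**Conclusion.** The point stands in a limited form. Non-significance on these ANOVAs would not show that the lunches were rated equally. At N = 32, a 0.5 SD difference on one rating goes undetected in 18–31% of trials at ρ = 0.5, and the figure depends heavily on a correlation the documents do not give. The trigger for adjustment is undefined and, if any scale suffices, unreliable in both directions: off in about 12–22% of trials with a real pleasantness difference (ρ = 0.5), on in about 24–35% with none. It also gives Sweet or Soft the same standing as Pleasant.

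The main harm is to interpretation. A statement of equal ratings would lack support just where the medium-to-high fall in grams needs it. Inflation of false positives is a minor part of the problem.

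**What to change.** In Primary analyses, report the paired differences (low–medium, medium–high, low–high) in each sensory rating with 95% confidence intervals, and state that a non-significant ANOVA will not be described as equal ratings.

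In Sensitivity analyses, remove the significance trigger. Name Pleasant and Appetising (visually) as the palatability covariates and run the adjusted analysis whatever the ANOVA p-values. Keep it as a sensitivity analysis, with a caveat: ratings are taken after eating, so energy density or the amount eaten may affect them, and adjusting may remove part of the effect under study or introduce bias.

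A pass/fail margin such as ±10 points should not be imposed. It has no source in the documents. If the intervals for all three pairs on both palatability scales had to lie inside it, identical meals would pass in only about 0–1% of trials at ρ = 0.3, 0–14% at 0.5 and 12–63% at 0.7 (assumed rating SD 20–25, correlation between the two scales 0.5–0.8).

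The cost is some wording and one extra analysis of data already being collected. The downside is imprecision. The interval half-width is 2.04 × SD × √(2(1 − ρ)) / √32, or about 6–11 points for SD 20–25 and ρ 0.3–0.7, so the trial may have to report that similar palatability was not established.

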DINNER	
After completing hunger and fullness ratings and a cognitive task again, participants will be provided with a glass of water and a ready-meal for dinner, which they can serve themselves.
 
After dinner, participants will be provided with a dessert to have as much or as little of as they like.
	
After completing hunger and fullness ratings and a cognitive task again, participants will be provided with a glass of water and a ready-meal for dinner, which they can serve themselves.
 
After dinner, participants will be provided with a dessert to have as much or as little of as they like.
	
After completing hunger and fullness ratings and a cognitive task again, participants will be provided with a glass of water and a ready-meal for dinner, which they can serve themselves.
 
After dinner, participants will be provided with a dessert to have as much or as little of as they like.

POST-MEAL	Participants will complete hunger and fullness ratings and a cognitive task again.	Participants will complete hunger and fullness ratings and a cognitive task again.	Participants will complete hunger and fullness ratings and a cognitive task again. Participants will complete measures of satiety responsiveness (Appendix F) and compensatory health beliefs (Appendix G).
DEBRIEFING			Aim guessing in an open-ended response format will be provided to participants (Appendix H). Following this, participants will be asked to rank the meals from the three weeks in order of energy density. Participants will be debriefed on study aims (Appendix H).
DATA MANAGEMENT	
The result files will contain:
 
 ○ Participant unique ID (randomly generated) ○ Demographic and questionnaire data ○ Amount of each lunch meal consumed (g) ○ Energy consumed for each lunch (kcal) ○ Snacks consumed ○ Amount of dinner and dessert consumed (g) ○ Energy consumed for dinner and dessert (kcal) 		

Analysis Plan

Participant characteristics:

Only participants who have completed the entire study (all three visits) will be included in analysis. We will report analyses with any participants who guess the aims of the study included and excluded.

If any participants do not follow study instructions (e.g. do not consumer any or only a very small amount of any of the food (<50kcal) then they will be removed from primary analyses.

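### Comparing significance in participants who do and do not rank the meals correctly would often suggest that awareness matters when it does not; test the difference directly and report estimates with intervals

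*Combined protocol and SAP*

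**What the plan says.** Under Analysis Plan, Sensitivity analyses, the plan states: "We will report whether sensitivity analyses deviate from primary analyses (e.g. if significant findings become non-significant and vice versa". No other criterion for a deviation appears.

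The checks fall into three kinds.

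- **Subgroup comparison.** The plan will "examine if results remain the same among participants who accurately identify the differences in energy density between foods vs. participants who do not". It gives no expected subgroup sizes and no test of the difference. There is an alternative: when few people fail to rank the meals correctly, the analysis is repeated without them. What counts as few is not defined.
- **Exclusion.** Under Participant characteristics: "We will report analyses with any participants who guess the aims of the study included and excluded". No expected number is given.
- **Checks that keep everyone.** For outliers, "for any outcomes identified as outliers we will examine the effect of winsorizing the outlier". If sensory ratings differ between meals, "we will also examine if results remain the same when sensory ratings are controlled for in analyses as a covariate".

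The Sample size section sets the minimum at 32, from post-hoc t-tests with d = 0.52 and 80% power (printed as 0.8%).

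**The concern.** The manipulation is meant to be covert, so whether recognising the energy density order changes the intake effect is a substantive question. The plan would answer it by seeing whether results hold in each group, and the only yardstick it names is significance.

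A study sized at about 80% power for pairwise tests has much less power in any part of its sample. One group reaching p < 0.05 while the other does not is therefore a common outcome even when the effect is the same in both. It is not evidence of a difference between them.

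The yardstick also misses things in the other direction. A large shift in an estimate would pass unremarked if both p-values stayed below 0.05. For the low-to-medium gram comparison, where the Hypotheses section expects little difference, a smaller sample makes non-significance more likely and so makes the result look stable.

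The grouping is blurred too. Three meals can be ordered in six ways, so one in six participants with no knowledge will rank them correctly.

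**Working it through.** **Inputs.** From Sample size: d = 0.52, 80% power, N = 32. From Inference criteria: p < 0.05 for primary analyses. Assumed: two-sided tests, d as the paired standardised difference, and the subgroup splits, which the documents do not give.

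**Reproducing the plan's figure.** Paired t-test power uses the noncentral t with df = n − 1 and noncentrality d√n. At n = 32 the noncentrality is 0.52 × √32 = 2.94 and power is 81.3%. At n = 31 power is just under 80%. So 32 reproduces.

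**Power in part of the sample, same d.** 28: 75.6%; 24: 68.4%; 20: 59.8%; 16: 49.5%; 12: 37.6%; 8: 24.7%. In any split of 32 the smaller group has at most 16, so its power is at most about 50%.

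**Chance that at least one subgroup loses significance.** The true effect is identical in everyone, the split is random and the full-sample result is significant. When both subgroups are significant the full sample almost always is as well, so the chance is close to 1 − (power A × power B) / 0.813. Simulation of the whole process agrees.

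| Split | Power A | Power B | Formula | Simulated |
|---|---|---|---|---|
| 16/16 | 0.495 | 0.495 | 0.699 | 70% |
| 20/12 | 0.598 | 0.376 | 0.723 | 72% |
| 24/8 | 0.684 | 0.247 | 0.792 | 79% |
| 27/5 | 0.739 | 0.148 | 0.865 | 87% |

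At 16/16, exactly one half is significant in 57% of cases, which is the pattern most easily read as an effect of awareness. A condition by identifier interaction test gives a false positive in 5% under the same conditions. The 27/5 row is roughly what chance alone would produce if nobody could tell the meals apart: 32 / 6 = 5.3 correct rankings.

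**Dependence on effect size, 16/16.** d = 0.35: 86%. d = 0.52: 70%. d = 0.8: 27%. At d = 0.8 the uneven splits give 34% (20/12) and 52% (24/8).

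**The ANOVA.** With f = 0.25, three measures, and correlation 0.5 and sphericity assumed, λ = n × 3 × f² / (1 − ρ). At n = 32, λ = 32 × 3 × 0.0625 / 0.5 = 12 and power is 86.6%; at n = 16, λ = 6 and power is 53.9%. At least one subgroup loses significance in 66% (16/16), 69% (20/12) and 77% (24/8).

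**Simple exclusions, d = 0.52.** Removing 2, 4, 6 or 10 participants at random turns a significant result non-significant in 5%, 10%, 14% and 24% of cases.

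**Precision of the direct comparison.** The 95% CI half-width for the difference between groups is t(0.975, 30) × √(1/n₁ + 1/n₂), in SD units of the paired difference. At 16/16 this is 2.042 × √(1/16 + 1/16) = 0.72 SD. Power is 30% for a difference of 0.52 SD and reaches 80% near 1.02 SD.

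**The case against.** Several points on the other side stand.

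- A reader might infer that the sample will be halved. The documents give no split, and they switch to simple exclusion when few participants fail to rank correctly, where the flip rate is only 5% to 10% for 2 to 4 removed. But 16/16 gives the lowest rate among the splits examined. The switch also does not cover the case where few participants rank correctly, which is what a successful covert manipulation would produce.
- A reader might infer that the checks are bound to deviate. They are not. At the previous study's partial eta squared of 0.4 (grams) and 0.7 (kcal), F-test power at n = 16 is 97.5% and about 100%, so flips would be rare. The Sample size section itself, however, anticipates smaller effects.
- A reader might say that 16 participants have half the power of 32. The figures are 49.5% against 81.3%, about 61% of the full-sample power.
- A reader might extend the point to every sensitivity analysis. Winsorizing and covariate adjustment keep all participants.
- The flip is introduced as an example, so it is not declared the sole rule. The plan also commits to reporting results with aim-guessers both included and excluded.
- These are sensitivity analyses, and the primary inference does not depend on them.

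None of this supplies a test of the difference between identifiers and non-identifiers, and that gap is what remains.

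**Conclusion.** The point holds for the identifier check. At the design effect, with no true difference between groups and a significant full-sample result, the separate-significance comparison would show at least one subgroup losing significance in 70% to 87% of cases across the splits examined. It would therefore often suggest that awareness changes the effect when it does not. This rests on d = 0.52 as a paired effect, two-sided tests at 0.05, and assumed splits; at d = 0.8 and 16/16 the figure is 27%.

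For simple exclusions the same weakness is present but smaller. For winsorizing and covariate adjustment there is no loss of sample, and the remaining issue is only that a p-value crossing 0.05 is a poor summary of change. The documents do not support a broader claim that the sensitivity analyses as a whole are unsound or that the primary conclusions are affected.

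**What to change.** - **Identifier check.** Replace the separate-significance comparison with one condition by identifier model. Report the interaction estimate, and each group's low-medium and medium-high differences, all with 95% CIs.
- **All other sensitivity analyses.** Report the condition differences with 95% CIs beside the primary estimates. Assess deviation on the estimates, not on whether p crosses the threshold.
- **No fixed percentage cut-off.** A 20% rule, for example, does no better. With d = 0.52 and a significant full sample, random removal of 4, 6 or 10 participants shifts the estimate by more than 20% in 10%, 19% and 34% of cases, against 10%, 14% and 24% for the flip criterion.
- **Ranking.** Report the observed correct-ranking rate against the one-in-six chance rate.

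The cost is a change of SAP wording and one extra model, with no new data. The drawback is imprecision. At N = 32 the interaction interval is about ±0.72 SD even for an equal split, with 80% power only for a difference near 1.0 SD. The plan should state this, so that an inconclusive interaction is not read as showing that awareness has no effect.

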A limitation of existing research is that it tended to examine the effects of manipulating energy density for relatively low energy dense foods and foods are manipulated covertly during a single session, so consumers are not able to learn about the energy content(14). For example, in the two studies mentioned, the highest energy densities tested were 1.8kcal/g(16) and 2.2kcal/g(15) respectively. However, consumers often are exposed to and consume foods of higher energy density. In one UK fast food restaurant menu, main meal items ranged from 1.9kcal/g to 3.2 kcal/g(17). This may be an important consideration because recent observational research suggested that up to approximately 1.5-2kcal/g, individuals are relatively insensitive to changes in energy density, and there is no indication of compensation through altering meal size(18). However, upwards of approximately 1.5-2kcal/g, the authors proposed that individuals compensate for increases in energy density by selecting and consuming smaller meal sizes. The proposed explanation for this is that individuals rely on the volume of food as the dominant signal with energy dilute foods (i.e.<1.5) and rely on calorie content as the dominant signal for energy rich foods(18). The volume signal is related to gastric distention and the calorie content signal is related to both learned and unlearned effects. If correct, the proposed model has implications for food product energy reformulation, as it suggests that reducing the energy density of more energy dense food products (e.g. >2.5kcal/g to 2kcal/g) may not lead to reductions in energy intake because within this range of energy densities consumers adjust meal size to compensate for changes in energy density.

However, there has been no formal testing of the proposed model using experimental approaches and it is unclear how efficiently consumers learn about the density of energy dense foods and adjust their meal size accordingly. In a previous study, we tested whether consumers adjust the meal size when given foods varying in energy density. This previous study measured the meal size of three desserts that were familiar to participants with the same basic ingredients (vanilla yoghurt, vanilla ice cream, vanilla cheesecake) but varying in energy densities (1.2kcal/g, 1.9kcal/g, 3.5kcal/g), with the aim of understanding the extent to which learned energy density would influence intake.

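### The pairwise tests that set N = 32 use the previous study's smallest effect unreduced, although smaller effects are expected, and the ANOVA gate takes power for the gram hypothesis just below 80%

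*Combined protocol and SAP*

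**What the plan says.** The Sample size section explains why effects should shrink: "As the relative energy density of the meals will be unknown to participants (desserts were familiar in the previous study"), and so "it is anticipated that effect sizes will be smaller than observed in the previous study". For the three-condition ANOVA it acts on this. The previous partial eta squared values were 0.4 for grams and 0.7 for kcal, and the plan states: "We will power the present study to be able to detect a medium effect size of $f = 0.25". That calculation gives 28.

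The next paragraph turns to the pairwise tests: "In the previous study, the smallest effect observed had a Cohens D of 0.52". The study is to "detect effects of this size at 0.8% power in post-hoc t-tests, which will require a minimum sample of 32 participants". The larger figure, 32, becomes the recruitment target. (I read 0.8% as 80%.)

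Under Primary analyses the pairs are conditional: "Where significant main effects are identified, post-hoc pairwise comparisons will be performed to identify where these differences exist". Under Inference criteria, "Results for primary analyses will be considered significant at $p<0.05"; no adjustment is stated for the primary pairs.

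The Hypotheses section predicts similar grams from low to medium with more kcal, then fewer grams from medium to high.

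**The concern.** Two adjacent paragraphs treat the same expectation differently. The expected shrinkage is applied to the ANOVA, which does not set the sample size, and not to the pairwise tests, which do. In addition, the pairwise calculation is for a test that is always carried out, whereas the planned test needs a significant ANOVA first.

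Hypothesis 2 rests on one comparison, medium against high in grams. A reader told that this comparison has 80% power would take a non-significant result as fairly good evidence that people do not reduce meal size at high energy density. Hypothesis 1 raises a related risk, because it predicts similar grams at low and medium density and a non-significant pair could be taken as support. How informative either result is depends on the power at effects the study might plausibly meet.

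**Working it through.** **Inputs.** From the Sample size section: d = 0.52, 80% power, N = 32, f = 0.25. From Inference criteria: alpha 0.05. From Study design: three conditions within subjects. Sidedness is not stated; two-sided reproduces the plan's figure.

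**Step 1: reproduce 32.** Paired t-test with n − 1 degrees of freedom and noncentrality d√n.
- n = 32: 0.52 × √32 = 2.94, power 81.3%.
- n = 31: power 79.997%, just short.

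The plan's figure reproduces exactly, with almost no slack. One-sided testing would give 25, and a Bonferroni alpha of 0.05/3 would give 42, so 32 is an unadjusted two-sided test at exactly d = 0.52.

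**Step 2: smaller effects, tested directly.** The plan states no amount of shrinkage, so these reductions are assumptions.

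| Reduction from 0.52 | d | Power at n = 32 | N for 80% |
|---|---|---|---|
| none | 0.52 | 81% | 32 |
| 10% | 0.468 | 73% | 38 |
| 20% | 0.416 | 63% | 48 |
| 30% | 0.364 | 51% | 62 |
| 50% | 0.26 | 30% | 119 |

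The effect detectable with 80% power at n = 32 is about 0.51.

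**Step 3: add the ANOVA gate.** Simulated trials, at least 40,000 per setting, n = 32, normal data, equal variances and equal correlations between conditions. Means follow the gram hypothesis: low = medium, high lower by d paired standard deviations. Success requires both the ANOVA and the medium–high paired t-test to reach p < 0.05. Assumed correlations of 0.5 and 0.7 give the same result.

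| d (medium–high grams) | Tested directly | After the ANOVA gate |
|---|---|---|
| 0.52 | 81% | 77–78% |
| 0.40 | 59% | 52% |
| 0.30 | 38% | 29–30% |

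The gate costs about 4 points at 0.52, 7 at 0.40 and 8 at 0.30. It depends on the pattern: if intake changes by equal steps across the three conditions, as could hold for kcal, the cost is under 1 point.

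**Step 4: what the reduced f implies for the same pair.** With two equal means and the third lower by D standard deviations, the standard deviation of the means is D√2/3. Setting this to 0.25 gives D = 0.25 × 3/√2 = 0.53. The paired effect is D/√(2(1 − correlation)):
- correlation 0.5: 0.53/1 = 0.53, direct power 83%;
- correlation 0.7: 0.53/√0.6 = 0.68, direct power 96%.

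So under the hypothesised gram pattern, the plan's own reduced ANOVA effect is compatible with a medium–high d of about 0.52 or more.

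**The case against.** The strongest reply has three parts. First, the plan's sentence is conditional: it promises power for effects of the stated size, which is true of a directly tested pair, and the same paragraph discloses that pairs follow the ANOVA. Nothing in the plan says that a null will be read as no effect. Second, 0.52 was the smallest previous effect. A contrast that was larger before could shrink and still reach it, and the documents do not say which contrast or outcome it came from. Third, Step 4 shows that 0.52 does not conflict with f = 0.25 under the hypothesised gram pattern. All three stand, and they limit the conclusion. They do not supply a reason in the plan for leaving 0.52 unreduced, and they do not remove the gate loss. On the third, a linear pattern would give an adjacent-pair d of only about 0.31 at correlation 0.5, but that is not the gram hypothesis.

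A reader might also infer more than the documents support:
- **That d should shrink in the same proportion as f.** Partial eta squared 0.4 gives f = √(0.4/0.6) = 0.816; 0.25/0.816 = 0.306; 0.52 × 0.306 = 0.16, with 14% power. This mixes two scales. The 0.816 already absorbs the within-person correlation, while 0.25 appears to be on the scale where correlation enters separately. Converted at correlation 0.5, 0.25 becomes √(0.25² × 3/(2 × 0.5)) = 0.43, so the ratio is 0.53, not 0.306.
- **That smaller density steps guarantee smaller effects.** The earlier desserts were "varying in energy densities (1.2kcal/g, 1.9kcal/g, 3.5kcal/g"). Table 1 totals for the whole lunch give 1470/1250 = 1.18, 2145/1250 = 1.72 and 3930/1250 = 3.14 kcal/g. The absolute steps are smaller (0.54 and 1.43 against 0.7 and 1.6), but the medium-to-high ratio is 1.83 against 3.5/1.9 = 1.84. With the other medium chilli entry in Table 1 (1170 kcal, not 1275), the ratio is 1.93. The argument depends on the scale and the entry chosen.

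**Conclusion.** The point holds in a limited form. The plan expects smaller effects, keeps 0.52 for the calculation that fixes N, and gives no reason. For hypothesis 2 the stated 80% is not delivered as the test is planned, even at d = 0.52: about 77–78% under the hypothesised gram pattern. If the medium–high gram effect is 0.40 or 0.30, gated power is about 52% or 29–30%.

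It would go too far to conclude that hypothesis 2 is underpowered on the plan's own expectation. That would need a stated amount of shrinkage and a link between 0.52 and the medium–high gram contrast, and the documents give neither. Beyond the gate loss of about 4 points, a shortfall is possible, not established. Nor does the gate result carry over to the kcal part of hypothesis 1, where intake may rise at both steps.

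The figures assume 32 completers, two-sided alpha 0.05, no adjustment across pairs, and, for the gate, normal data with equal correlations. The plan's arithmetic for 32 is correct; what needs attention is the choice of input and the description of the power.

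**What to change.** 1. Reword the Sample size section along these lines: *Thirty-two completers give 80% power for a paired standardised difference of about 0.51 or more when tested directly. Power is 59% at 0.40 and 38% at 0.30, and lower if the test is conditional on the ANOVA. A non-significant pairwise result will not be read as no effect.* Add a sentence on which contrast 0.52 came from and why it was kept.
2. In Primary analyses, name the medium–high gram comparison as a planned two-sided contrast at 0.05, tested whether or not the ANOVA is significant. As the single planned test for that outcome, it recovers about 4 to 8 points of power under the hypothesised pattern. The other gram pairs stay post hoc.
3. Optionally, name the low–medium kcal comparison as a planned contrast too. No power gain should be claimed for it if kcal rises at both steps.

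The cost is protocol wording and a less favourable power statement. No extra participants are needed.
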